### 3. Study Objectives and Endpoints

#### 3.1. Study Objectives

##### **Objective 1:**

The first objective of this trial is to evaluate 5-year clinical status of patients implanted with the coflex® device in conjunction with surgical decompression relative to decompression alone. This objective will be accomplished by a Bayesian test of superiority using Month 60 composite clinical success. The composite primary endpoint for this objective is in three parts:

1. At least a 15 point improvement relative to pretreatment baseline in the Oswestry Disability Index (ODI, range 0-100);
2. No reoperations, revisions, removals, or supplemental fixation at the index level(s);
3. No  $\geq 2$  injections or series of injections for any lumbar level\*\*, or nerve block procedures performed to treat spinal stenosis at any lumbar level(s) or a single injection within 12 months of the 5 year endpoint.

\*\* A series of injections is considered 2-3 injections performed between 24-hour and one week intervals designed to treat a single pain event. Secondary injections performed due to patient demand or recurrence of symptoms following the initial injection are considered separate injections and would constitute a study failure.

Additionally, a sensitivity analysis will be performed with the condition where lumbar injections occurring at any time between surgery and Month 60 will be considered a treatment failure.

A lumbar injection is defined as any deep injection into the spine, typically under image-guidance, of steroids and/or other pharmacologic agents (e.g., facet injections or epidural injections by the transforaminal, interlaminar, or caudal routes). Other types of injections are not treatment failures such as trigger point injections, intramuscular injection for systemic administration of steroids, dry-needling, prolotherapy, or acupuncture, but a sensitivity analysis will be performed including all types of injections.

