### **3.2.1. Discussion about Month 60 Composite Clinical Success (CCS)**

After careful consideration, handling of lumbar injections will differ between the Month 24 CCS and CCS endpoints determined post Month 24, and in particular, for the primary Month 60 CCS to be used in Objective 1 analyses. As with the IDE study, lumbar injections that occur prior to two years post operatively are defined as Terminal Treatment Failures, Month 24 composite clinical failures and further follow-up is censored when summarizing effectiveness endpoints (i.e., ODI, VAS, ZCQ, treadmill). This is designed to (1) produce a composite endpoint that is sensitive to early device failure and to (2) avoid bias arising from inclusion of clinical data that could be reflecting successful secondary treatment of a failed index treatment. A different approach seems advisable for the Month 60 CCS endpoint for use in this ‘real conditions of use’ study. The goal is to avoid classifying calling transient symptom management as a device failure unless there is subsequent re-operation or unless patient status is compromised as reflected in lack of an ODI improvement from baseline that is less than 15%. Therefore, for Month 60 CCS, lumbar injections occurring within 12 months of the Month 60 visit will indicate Month 60 CCS failure (as well as those within the first 24 months post-surgery). This is because a lumbar injection within 12 months of the Month 60 visit can confound the Month 60 assessment. Similarly, when determining intermediate CCS at Month 36 and Month 48, lumbar injections within 12 months of these clinic visits will indicate CCS failure for that time point, but not necessarily for subsequent time points. However, patients with 2 or more series of injections will be defined at terminal failures, that is, as a CCS failure at that time point and all subsequent timepoints.

As noted above, handling of lumbar injections will differ between the Month 24 CCS and CCS endpoints determined post Month 24, and in particular, for the primary Month 60 CCS to be used in Objective 1 analyses. In sensitivity analysis, lumbar injections occurring at any time between surgery and Month 60 will be considered a treatment failure. All other endpoints in the Month 60 CCS analysis remain identical in the sensitivity analyses.

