#### **4.6. Study Conduct**

The study will be performed in up to 20 study centers in the US (10 coflex sites and 10 control sites). All centers are experienced in the treatment of spinal stenosis with decompression surgery and with the coflex® Interlaminar Technology, but no site were included in the IDE study. Each site will enroll either coflex patients or control patients. Sites will be selected for comparability in terms of surgeon and institutional characteristics as well as for expected patient mix characteristics. All treatments will be carried out according to the routine procedures for decompression surgery in each center. Only investigators that are experienced in the implantation of the study device will perform the surgeries for this trial.

Subjects participating in this study will be recruited from the investigators' standard patient populations. Subjects must meet all of the following inclusion criteria and none of the exclusion criteria. The investigator maintains exclusive responsibility for the inclusion and exclusion of any potential study participant.

All patients presenting for treatment of symptomatic spinal stenosis that have not responded to conventional medical therapy will be evaluated for study participation based on the inclusion/exclusion criteria. Subjects will be considered enrolled in the study after informed consent has been signed and at time of surgical incision.

The target enrollment is 406 patients (186 coflex patients and 220 decompression control patients). A minimum of 345 patients are planned to be included in the trial. Each center should recruit at least 5 patients.

The schedule of study related actions is summarized in the Study Timeline (see Section 4.8.9).

Patients who fulfil the in-/exclusion criteria will be enrolled into one of the two concurrent treatment groups.

Group A: decompression surgery without any further stabilization (control group)

Group B: decompression surgery with stabilization using the coflex® Interlaminar Technology (treatment group)

Blood sampling is not planned as a part of the trial but might be performed as part of the routine procedures of each center. Blood parameters will not be documented in the CRF – except if necessary for SAEs.

For the implantation of the coflex® Interlaminar Technology the product brochure and implantation instructions provided by the manufacturer have to be followed.

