#### **4.7.10. Follow Up Treatment after Discharge**

There are no study related limitations to the routine follow up treatment (e.g., use of orthoses, physiotherapy). The follow up treatment will be recorded in the eCRF until Visit 8.

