### **5.1.2. Secondary Surgical Interventions**

Reoperations, revisions, removals and supplemental fixation are defined as follows:

- A revision is a procedure that adjusts or in any way modifies or removes part of the original implant configuration, with or without replacement of a component. A revision may also include adjusting the position of the original configuration.
- A removal is a procedure where all of the original system configurations are removed with or without replacement.
- A reoperation is any surgical procedure at the involved level(s) that does not remove, modify, or add any components to the system. Note: a surgery to alleviate post-operative superficial wound problems within the immediate post-operative 30 day window will not be considered a treatment failure.
- A supplemental fixation is a spinal procedure in which additional instrumentation not under study in the protocol is implanted (e.g., supplemental placement of a rod/screw system or a plate/screw system) at the index level(s).

If a subject in either study group undergoes a reoperation, revision, removal, or supplemental fixation procedure, the subject should remain in the study and should continue to be followed up within the study. Such patients will be considered a Treatment Failure.

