## 7. Statistical Analysis

### 7.1. Accounting for Non-Randomized Treatment Group Comparisons

This study design includes concurrently enrolled, but non-randomized investigational and control arms. Covariate balance will be achieved using sub classification based on propensity score (PS) quintiles. The PS subclasses will be determined by an outcomes-blinded statistician soon after prospective enrollment is completed and before most if not all patients are evaluable for the two-year effectiveness endpoint. The process of assigning patients to subclasses will be submitted to FDA for review and acceptance prior to unblinding of the PS statistician. Selection into a PS subclass is the observational study equivalent to randomization. Subclasses will be determined using methods summarized below to ensure that within subclass, groups are well balanced for a rich set of clinically relevant baseline covariates. Analyses will proceed as if patients were

randomized to treatment group within subclass and effectiveness outcomes will be compared between groups using methods that account for PS subclass. There is a compelling case to be made that informative prior Bayesian designs are especially appropriate for post approval studies (PAS) since recent rigorous objective data is available. To make use of this prior information, a Bayesian design with informative priors has been specified for each Objective. For these Objectives, patient-level data from the IDE study are used to formulate the PAS prior distributions.

To make use of the beta-binomial updating from prior to posterior it is necessary to have counts of the numbers of successes and failures observed among the prospectively enrolled patients for both groups. These counts are added to prior beta distribution parameters that reflect (what amounts to) the prior numbers of success and failures. Combined, these sums of successes and failures determine the Bayesian posterior distribution. The simplicity of this approach stems from the mathematical convenience of conjugate priors which have, in addition to computational convenience, the practical advantage of being interpreted as additional data (Gelman, 2014). However, the numbers of successes and failures observed from each group to be used to update the prior distribution must account for the propensity subclass design.

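### Sites enrol one arm only and no planned analysis sets lumbar injections aside, so a difference in injection habit between the two sets of sites cannot be separated from a treatment effect

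*Combined protocol and SAP*

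**What the plan says.** **Design.** Section 4.6: "Each site will enroll either coflex patients or control patients". Section 7.16 accepts that site heterogeneity in relative effectiveness cannot be evaluated, and looks at site variability within each arm only. On follow-up care, section 4.7.10 says "There are no study related limitations to the routine follow up treatment", and no section gives criteria for a lumbar injection. The only blinding described is that of the PS statistician (section 7.1: "The PS subclasses will be determined by an outcomes-blinded statistician soon after prospective enrollment is completed"). The PS table in section 7.17.2 includes surgeon specialty, prior treatment and pain management, but nothing on how readily a site injects.

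**Scoring.** Section 3.2.1 treats a lumbar injection before two years as a terminal treatment failure, and adds that "further follow-up is censored when summarizing effectiveness endpoints (i.e., ODI, VAS, ZCQ, treadmill". Before Month 24, then, the event both fails the composite and removes later scores. For Month 60, the same section fails an injection in the first 24 months, an injection within 12 months of the visit, or two or more series. A single series between about Months 24 and 48 is neither a Month 60 failure nor said to be censored.

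**Sensitivity analyses.** One counts any lumbar injection up to Month 60 as failure (Objective 1B; section 3.2.1). Another widens the injection types (section 3.1, Objective 1: "but a sensitivity analysis will be performed including all types of injections"). The treadmill composite in section 7.8 replaces only the ODI item. Section 7.14 describes incremental composites that may be used and that add criteria.

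**The concern.** An injection is partly an outcome and partly a decision. Patients with poor results are more likely to receive one, but practices can also differ in when they offer it. In a trial with both arms at each site, habit would be roughly shared between arms. Here it is nested in arm, and PS subclassification cannot balance a practice that it does not measure.

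The two uses of the injection pull in opposite directions. The composite penalises the arm whose sites inject more. Censoring drops that arm's injected patients from the ODI, VAS, ZCQ and treadmill summaries and so flatters its means, if injection follows poor response. If the composite and the means disagreed, the plan has no analysis to show whether patient outcome or injection practice was the reason. Objectives 2 and 3 are exposed directly. Objective 1 is exposed to the extent that injections decide Month 60 status.

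**Working it through.** **Inputs from the plan.** 150 patients per arm; posterior threshold 0.95; coflex priors beta(82.1, 62.1) at Month 60 and beta(135.5, 69.5) at Month 24 (sections 7.7.1, 7.7.2); assumed coflex success 0.57 and 0.662. Control prior: beta(1, 1) for Objective 1 (formula in section 7.11.1) and beta(0.5, 0.5) for Objectives 2 and 3 (section 7.7.2).

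**Method.** For success counts s (coflex) and t (control), the rule declares superiority when P(θ_C > θ_D | s, t) ≥ 0.95, with θ_C ~ beta(a + s, b + 150 − s) and θ_D ~ beta(c + t, d + 150 − t). The chance of declaring is the sum, over all (s, t) that meet the rule, of Bin(s; 150, p_C) × Bin(t; 150, p_D). Crude counts stand in for the PS-adjusted counts.

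**Step 1: the plan's own figures.** Objective 1: power 82.3% at 12.5 points (stated 83%) and 64.7% at 10 points (stated 65%); type 1 error 3.6% (stated 3.7%). Objective 3: 86.1% at 12.5 points (stated 88%), 69.8% at 10 points (stated 73%), type 1 error 3.5% (stated below 5%). Objective 1 reproduces closely. Objective 3 comes out 2 to 3 points lower, which does not affect the comparison below.

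**Step 2: an illustrative habit gap (assumed rates).** Suppose 72% of patients in both arms would succeed if injections were ignored, and 8% of these are injected at coflex sites: 72% × 0.92 = 66.2%. If control sites inject 13% or 18% of them, the Month 24 gap is 72% × 0.05 = 3.6 points or 72% × 0.10 = 7.2 points, with no device effect.

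| Excess control failures from habit | Chance of Objective 3 superiority |
|---|---|
| 0 | 3.5% |
| 2 points | 9.2% |
| 3.6 points | 17% |
| 5 points | 26.6% |
| 7.2 points | 45% |

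For Objective 1, gaps of 2, 3.1 and 6.2 points give 8.7%, 13.1% and 32.7%, against 3.6% with no gap. These apply only as far as injections decide Month 60 status, and on that the sections differ (see the fix).

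**Step 3: the other direction.** If coflex sites cause 5 extra points of failure, Objective 3 power at a true 12.5 points falls from 86.1% to 71.9%. With the 7.2-point gap reversed and no true difference (59.0% against 66.2%), false superiority falls to 0.6%.

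**Step 4: censored means (assumed rates).** If a fraction f is injected and those patients score d points worse, censoring removes f × d from that arm's deficit. With 20% against 10% injected and d = 10 to 20 ODI points, the difference moves by (0.20 − 0.10) × 10 to 20 = 1 to 2 points, in favour of the arm that injects more.

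**Step 5: the prior for an injection-free composite.** The beta(135.5, 69.5) prior comes from an endpoint that fails injected patients. With 72% success in both arms (108 of 150), the coflex posterior mean is (135.5 + 108)/(205 + 150) = 68.6%, and the control mean is (0.5 + 108)/151 = 71.9%. Under that prior, false superiority is 0.4% and power at 72% against 59.5% is 64%. With beta(0.5, 0.5) in both arms the figures are 5.0% and 74%. Reusing the planned prior would make a real effect look like a practice effect.

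**The case against.** The strongest reply is that section 3.2.1 gives a sound reason for censoring: scores after an injection may reflect successful secondary treatment of a failed index procedure. This stands. An all-data mean credits rescue to the arm that uses it more, so it should be supportive and should not replace the censored summary.

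The plan also has mitigations. Section 4.6 says "Sites will be selected for comparability in terms of surgeon and institutional characteristics as well as for expected patient mix characteristics", and the PS list covers prior treatment, pain management and surgeon specialty. These may narrow a habit gap, but none of them measures one.

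Four stronger readings are tempting, and the documents do not support them:

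- *Every injection is failed or censored.* Not so for a single series between about Months 24 and 48.
- *No planned analysis would show an injection imbalance.* Section 5.1.3 captures all lumbar injections, section 6 assesses epidurals, and section 7.13 tabulates failure times by arm. These would show a gap, though they could not attribute it.
- *No secondary endpoint can act as a check.* EQ-5D is not on the censoring list, and section 7.14 evaluates Month 24 narcotic use as an outcome alone.
- *The plan favours coflex.* Nothing in the documents fixes the direction.

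Surgeon discretion and knowledge of arm are inferences from one-arm sites, from the absence of injection criteria, and from the absence of any other blinding statement. The examples in section 4.7.10 are orthoses and physiotherapy, not injections.

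**Conclusion.** The point holds as a gap in the supportive analyses. Injection practice is nested in arm and unmeasured, and no planned analysis keeps post-injection ODI, VAS, ZCQ or treadmill scores or takes injection out of the composite. Both injection sensitivity analyses count more injections as failure, so they can enlarge a practice effect but cannot remove it.

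The size is conditional. An excess of 2 points of habit-driven control failure would take the false-superiority chance to about 9% for Objectives 1 and 3; 3.6 and 7.2 points give about 17% and 45% for Objective 3. These figures assume that the excess injections fall on patients who would otherwise have succeeded. Excess injections in patients who miss the ODI criterion anyway add nothing to the composite gap. The documents give no injection rates, so the figures show sensitivity and do not predict bias. The change should be made, but it does not call the primary endpoint definition into question.

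**What to change.** 1. **Sections 3.2.1 and 7.9.** Keep the censored summaries. Add a pre-specified supportive summary of ODI, VAS, ZCQ and treadmill at Months 24 and 60 on all observed data regardless of injection, with 95% intervals.
2. **Objectives 1 to 3.** Add a sensitivity CCS without the injection item and with each objective's other items unchanged, PS-adjusted as planned. Use a non-informative prior in both arms, or a coflex prior re-derived from the IDE patient-level data (which section 7.1 says underlie the priors) on the same injection-free definition. Do not reuse beta(135.5, 69.5) or beta(82.1, 62.1).
3. **Reporting.** Show injection rates by site as well as by arm beside the primary result.
4. **Reconcile** section 3.2.1, which fails Month 60 for an injection in the first 24 months, with the Month 60 lists in sections 3.1, 3.2 and 5.1, which do not list a single early injection as a failure.

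**Cost.** SAP text, a few tables and, if chosen, one re-derived prior. No change to care or visits is involved. All lumbar injections are already captured, and no section withdraws injected patients, although continued follow-up is explicit only after secondary surgery (section 5.1.2: "the subject should remain in the study and should continue to be followed up within the study"). The drawback is that all-data means include some benefit from rescue, so they stay supportive.

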### 3.3. Secondary Endpoints

- ODI change compared to baseline at 24 and 60 months as a continuous variables and in terms of achieving at least a 15 point improvement.
- Change in Visual Analog Scale (VAS) for low back pain (on the 100 mm scale) after 24 and 60 months compared to baseline as a continuous variables and in terms of achieving a 20 point improvement.
- Change in right and left leg pain using a Visual Analog Scale (VAS) 100 mm scale after 24 and 60 months compared to baseline as a continuous variable and in terms of achieving a 20 point improvement. A separate analysis will be performed to compare VAS scores for the “worst” legs.
- Change of Zurich Claudication Questionnaire (ZCQ) after 24 and 60 months compared to baseline:
  - Symptom severity (range 1-5)
  - Physical function (range 1-4)
  - Patient satisfaction (range 1-4, no baseline).
  - ZCQ Overall Success ( $\geq 2$  of 3 of the following)
    - Improvement in symptom severity  $\geq 0.5$
    - Improvement in physical function  $\geq 0.5$
    - Satisfied or somewhat satisfied as defined by a score of  $\leq 2.5$  points on the patient satisfaction domain.
  - ZCQ Overall Success components
- Maintenance or improvement in EQ-5D compared to baseline
- Change from baseline to Month 24 and Month 60 in maximum walking time from treadmill test as a continuous variable and in terms of achieving at least an 8 minute improvement or maximum time of 15 minutes.
- Change from baseline to Month 24 and Month 60 in time to symptoms from treadmill test as a continuous variable and in terms of achieving at least an 8 minute improvement or maximum time of 15 minutes.
- Neurological status (no new or worsening, persistent neurological deficit)
- Radiography Endpoints
  - Assessment of significant migration of the implant or the complete expulsion (significant is defined  $> 5$  mm).
  - Assessment of spinous process fracture.
  - Assessment of maintenance of foraminal height
  - Assessment of adjacent level disease determined by independent radiographic review
- Correlation of foraminal height changes to improvement of walking distance on a treadmill (after 24 and 60 months compared to baseline).

 Pratt RK et al., The Reliability of the Shuttle Walking Test, the Swiss Spinal Stenosis Questionnaire, the Oxford Spinal Stenosis Score and the Oswestry Disability Index in the Assessment of Patients with Lumbar Spinal Stenosis. Spine Vol. 27 (1) pp. 84-91.

 Stucki G et al., Measurement Properties of a Self-Administered Outcome Measure in Lumbar Spinal Stenosis. Spine. Vol. 21(7). pp. 796-803.

- The CCS will be modified to examine the effect narcotics use (opioids and/or opiates) has on treatment success rates. When comparing coflex® in conjunction with decompression to decompression alone, this modified Month 24 CCS will include:
  - No “Treatment Failure” on or before the exact 2-year anniversary of the index surgery. Treatment Failure will include:
    - No surgical intervention at the index level
    - No lumbar epidural steroid injection including nerve root blocks and facet blocks at any lumbar level
  - No persistent new or worsening sensory or motor deficit where persistence is established by identifying new or worsening deficits at Month 12 that do not resolve by Month 24.
  - No major device-related adverse event defined as an event simultaneously both ‘Serious’ and ‘Definitely’ according to independent Clinical Events Committee (CEC) related to the implant on or before the exact surgical two-year anniversary or exact five-year anniversary. In the decompression alone group, since there is no device, this endpoint will be identified as any serious AE that is classified as definitely related to surgery.
- No use of a narcotic (opioids or opiates) at Month 24.

